1. PROTOCOL SUMMARY

1.1 Synopsis

Rationale for Proposed Clinical Study

COVID-19 has rapidly emerged as a life-threatening pandemic globally. Experience with SARS-CoV-2 indicates that approximately 14% develop severe disease that requires hospitalization and oxygen support, and 5% require admission to an intensive care unit. In severe cases, COVID-19 can be complicated by acute respiratory distress syndrome (ARDS), sepsis and septic shock, multiorgan failure, including acute kidney injury and cardiac injury. Although SARS-CoV-2 can infect the respiratory tract and cause direct cytolytic damage, these actions only partially explain the disease pathology. The majority of tissue damage appears to be driven by cytokine release syndrome (CRS) mediated host inflammatory response, which may occur even in patients who appear to be resolving infection by viral titers. Studies have shown that moderate to severe cases of COVID-19 are characterized by marked inflammation and cytokine storm.⁽¹⁻⁵⁾ These conditions may make it difficult to modify COVID-19 disease pathology solely with pathogen-directed therapeutics such as remdesivir or viral neutralizing monoclonal antibodies. Therefore, it is imperative for any treatment strategy to consider host-directed mechanisms that mitigate CRS and the hyperinflammatory immune response. Thus, combining pathogen-directed and host-directed therapeutics may have more utility and play a critical role in reducing the morbidity, mortality, need for invasive mechanical ventilation (IMV) and duration of hospitalization.

Lenzilumab is a monoclonal antibody (mAb) that acts to reduce CRS through granulocyte-macrophage colony-stimulating factor (GM-CSF) neutralization. Extensive data shows GM-CSF to be a key upstream cytokine in the initiation of CRS and neutralization of GM-CSF is expected to prevent or reduce the severity of CRS. In preclinical models of CRS induced by CAR-T and graft versus host disease, activated T cell production of GM-CSF licenses myeloid cells to expand and produce downstream inflammatory cytokines such as IL-1b, IL-6, MCP-1, MIP1a, IP-10, and TNF α . Neutralization of GM-CSF prevents the development of CRS and results in decreased levels of IL-6, MCP-1, MIP1a, IP-10, and TNF α and reduced levels of inflammatory myeloid cells. These and other data indicate that GM-CSF is a critical upstream regulator of many downstream inflammatory cytokines known to be important in the pathophysiology of CRS.

[figure not shown]
In COVID-19, emerging clinical data point to the abundance of aberrant pathogenic GM-CSF+ T-cells in patients with severe disease and the frequency of GM-CSF+ CD8 T cells, GM-CSF+ CD4 T cells, IFNg+ GM-CSF+ CD4 T cells, and inflammatory CD14+CD16+ monocytes are correlated with severe disease and ICU admission. GM-CSF appears to play a role in the activation, expansion, and trafficking of inflammatory myeloid cells that make up the majority of the inflammatory cell infiltrate as measured by bronchoalveolar lavage in patients with severe COVID- 19.

Lenzilumab has already been studied four phase I/II clinical trials across various indications, including patients with severe asthma, and has a favorable safety and tolerability profile. There have been no dose-limiting toxicities, no treatment-related severe adverse events or grade 3 or 4 events, and no discontinuations due to adverse events reported to date with lenzilumab.

An initial cohort of patients with severe and critical COVID-19 pneumonia treated with lenzilumab under single use emergency INDs was conducted. Twelve patients were treated with lenzilumab, 600 mg IV every 8 hours for a total of three doses within a 24-hour period. It is important to note that this dosing regimen was specifically developed for the prevention and treatment of CRS (aka cytokine storm). The control cohort was identified from an electronic registry of more than 1,900 patients with confirmed COVID-19 in the same centers as lenzilumab cases. The control cohort is comprised of 27 patients who were not treated with lenzilumab, but were matched to cases in age, gender, comorbidity (at least 1 risk factor for poor outcome from COVID-19), as well as for being hospitalized with COVID-19 pneumonia, requiring oxygen supplementation without mechanical ventilation. At the time of their selection for the control cohort, the clinical outcomes of these patients were not known.

Patients treated with lenzilumab demonstrated rapid improvement in oxygenation as determined by differences in mean SpO₂/FiO₂ ratios which were statistically significant ($p<0.001$, [Figure 1](#)). There was also a statistically significant difference in the time to resolution of ARDS ($\text{SpO}_2/\text{FiO}_2 < 315$, $p<0.001$).

Figure 1. Improvement in oxygenation and time to resolution of ARDS in patients treated with lenzilumab and controls

Lenzilumab treated patients also showed a statistically significant improvement in CRP on day 3 post treatment relative to controls ($p=0.014$; see [Table 1](#)). Absolute lymphocyte counts (ALC) also showed a statistically significant improvement post lenzilumab relative to control ($p=0.04$, [Table 1](#)).

[figure not shown]
Table 1. Change in CRP and ALC in patients treated with lenzilumab and controls

Table 3. Laboratory Markers	Lenzilumab group (n=12)	Control group (n=27)	P-value
CRP reduction	135.8	-0.95	.01
IL-6 reduction	20.1	na	na
ALC increase	$0.46 \times 10^9/\text{L}$	$0.03 \times 10^9/\text{L}$.04
PLT increase	52.5	63.2	.61

Median time to 2-point clinical improvement on the 8-point clinical status ordinal scale was five days in the lenzilumab cohort vs. 11 days in the control group ($\chi^2=7.43$, $p=0.006$; see [Figure 2](#)). Ventilator-free survival trended in favor of lenzilumab ($\chi^2=3.67$, $p=0.06$, [Figure 2B](#)).

Progression to invasive mechanical ventilation was 8.3% in the lenzilumab cohort vs. 37.0% in the control group ($p=0.10$). Mortality rate was 8% in the lenzilumab cohort vs. 19% in the control group ($p=0.43$).

[figure not shown]
Figure 2. Clinical improvement in patients treated with lenzilumab and controls

Concurrent with the implementation and enrollment of BET-B, the lenzilumab manufacturer, Humanigen, sponsored a phase 3 randomized, double-blind, placebo-controlled trial in hospitalized patients with COVID-19. Five hundred twenty subjects age >18 years, hospitalized with COVID-19 and with either oxygen saturation $\leq 94\%$ on room air and/or requiring supplemental oxygen, were enrolled. (i.e., ordinal score 5 or 6 in the BET-B trial). The study excluded those on invasive mechanical ventilation (i.e. ordinal score 7 in the BET-B trial). Subjects were randomized to receive lenzilumab (1800 mg, $n=261$) or placebo ($n=259$) via three intravenous infusions administered 8 hours apart. As part of standard of care, 93.7% of subjects received corticosteroids, including dexamethasone, 72.4% received remdesivir, and 69.1% received both. Baseline demographics were comparable between the two treatment groups.

The primary endpoint was survival without mechanical ventilation (SWOV) through day 28, using a time to event approach. The Kaplan-Meier (KM) estimate of failure to achieve SWOV by Day 28 was 15.6% (11.5-20.9) in the lenzilumab group compared to 22.1% (17.4-27.9) in the placebo group (Hazard Ratio [HR] = 1.54, $p=0.0403$, mITT; [Figure 2A](#)).⁽⁶⁾ In a post hoc analysis, the subgroup of subjects with a CRP < 150 mg/L and age < 85 years, the KM estimate of failure to achieve SWOV was 8.5% (5.0-14.1) in the lenzilumab group compared to 21.2% (15.9-28.1) in the placebo group (HR=2.96, $p=0.0003$, mITT; [Figure 2B](#)). A similar treatment effect was observed when evaluating those that received remdesivir (15.6% vs 25.7%, HR=1.91, $p=0.0073$, mITT) as well as remdesivir + steroids (16.3% vs 26.9%, HR=1.92, $p=0.0067$, mITT). Mortality in the full population did not reach a statistically significant difference (9.5 in lenzilumab arm vs 13.9% in placebo, HR=1.38, $p=0.241$), but in the subgroup of subjects with a CRP < 150 mg/L and age < 85 years this was statistically significant (6.5% vs 13.8%, HR=2.2, $p=0.033$, no adjustments for multiple comparisons).

Figure 3. Kaplan-Meier plot of Survival Without Ventilation. A. Plot for mITT population. B. Plot for mITT population with baseline CRP<150 mg/L .

Based on the results from the LIVE-AIR trial (and with no knowledge of unblinded interim results from this trial), consideration was made to expanding BET-B from a phase 2 to a phase 2/3 to serve as a confirmatory pivotal trial. This could be accomplished with a larger sample size. These changes were implemented in v5 of the protocol.

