9.1 Sample Size Determination

The LIVE-AIR trial estimated a HR of about 1.5 in its overall population, and a HR of above 3 in the identified subgroup. The corresponding relative risks for the primary endpoint were in the 2.5 or 2.6 range, and the corresponding odds ratio were around 3. Because the treatment effect in the post hoc subgroup may be overly optimistic, the BET-B updated sample size assumes an intermediate odds ratio of 2.5 for the subgroup. The LIVE-AIR trial also observed a 21% event rate in the placebo group in the subgroup, which is likely higher than expected in this trial. (The primary analysis, logistic regression, will estimate an odds ratio. For the expected range of control event rates, the relative risk of 2.2 corresponds to an odds ratio of about 2.5; the relevant observed odds ratios in LIVE-AIR were about 3.)

A sample size of 400 in the subgroup will yield 80% power if the control event rate is 16% and 89% power if the control rate is 21%, if the odds ratio is 2.5 and a two-sided alpha=.049. (An odds ratio of 2.5 is defined such that if the control event rate is 16%, the treated rate would be 7%). At most 550 participants (that is, subjects randomized into BET-B and relevant shared controls) will be randomized. Based on early BET baseline estimates, roughly 75% of subjects are expected to fall in the primary analysis subgroup at baseline (CRP<150, age<85, and OS<7). The trial will enroll subjects until 400 are randomized in the subgroup or 550 overall, whatever comes first. These calculations are not inflated for missing data, as little missing data are expected.

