	Subgroup	
Repeat the primary analysis for this endpoint within each of the following subgroups using the ITT population:
 
 
• Actual baseline ordinal score
 
• Baseline steroid use
 
• Baseline use of emerging COVID-19 treatments
 
• Duration of symptoms prior to enrollment
 
• Race
 
• Ethnicity
 
• Comorbidities
 
• Age (categorical)
 
• Sex
 
• Baseline CRP (<math>\leq</math> median, <math>></math>median)
 
• Baseline CRP (<math><150</math>, <math>\geq 150</math>)
 
 
Baseline dexamethasone use, baseline CRP (continuous), age (continuous), and baseline ordinal score will be included in the subgroup analysis as covariates unless the covariate is the subgroup.

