### 8.1.3. Secondary Analysis for the Primary Endpoint

A secondary analysis of the primary endpoint will be performed using a targeted maximum likelihood estimate (TMLE) method for binary outcomes that estimates the average treatment effect among the entire population in terms of an odds ratio with corresponding p-value will be used. The test decision for this secondary analysis will be based on the p-value of the marginal odds ratio.

For the underlying estimation of the binary outcome variable in each treatment arm, the following baseline covariates will be utilized:

- Actual baseline ordinal score
- Age (continuous)
- Sex
- Race and Ethnicity (Black or Hispanic indicator)
- Baseline CRP
- Baseline lymphocyte count
- Baseline D-dimer
- Baseline creatinine
- Use of dexamethasone
- Chronic respiratory disease
- Chronic kidney disease
- Cardiovascular disease
- Comorbidities (Indicator for 2 or more comorbidities)

The following super learner libraries with logistic link functions will be applied:

- SL.glm (generalized linear model)
- SL.gam (general additive model using smoothing splines of degree 2 for continuous variables)
- SL.glmnet (generalized linear model with Lasso regularization, deviance as loss function and applying the lambda with minimal deviance for the prediction).

Categorical covariates with 90% of the subjects in one category will be dropped from the TMLE analysis. Mean imputation will be used for subjects missing values for continuous baseline variables. Missing values for categorical variables will be given a value of 'No'. No missing data is expected for baseline ordinal score

Odds ratio (treatment vs. placebo) = marginal odds ratio comparing the odds of patients with treatment vs. placebo in terms of who survived without ventilation up to and including Study Day 29.

Marginal odds ratios, corresponding 95% CIs, and a p-value from an TMLE will be presented. Additionally, marginal risk differences with corresponding 95% CI will be presented.

Missingness in the outcome is accounted for in the estimation procedure of TMLE using the missing indicator as shown in the below pseudocode. The TMLE approach will be implemented using the tmle R package (<https://cran.r-project.org/web/packages/tmle/index.html>).

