c Sensitivity Analysis 2: Odds Ratios of Active treatment vs Placebo calculated from the logistic regression model adjusted for baseline dexamethasone use, baseline OS, age (continuous), and baseline CRP. Subjects without event whose last assessment is in window for Day 29 (Day 26, 27, 28) are considered missing. Missing data imputed using the 3-stage imputation procedure described in Section 6.5.												
d Sensitivity Analysis 3: Same imputation as initial model in a . The final model also includes categorical age and geographical regions as covariates.												
e Sensitivity Analysis 4: PROC MI part of the imputation model uses FCS logistic instead of monotone logistic. The rest of the imputation procedure and final covariates are similar to those in the initial model in a .												
f TMLE Approach 1: Estimates marginal ORs and risk differences using TMLE and adjusts for all missing data using the missing indicator functionality of TMLE.												
g TMLE Approach 2: Estimates marginal ORs and risk differences using MI combining TMLE analysis in imputed datasets. Missing events for discharged subjects are considered non-events, missing events for subjects with no post baseline data are handled using the missing indicator in TMLE, while a similar MI procedure as the primary analysis is used to impute missing event for subjects who were hospitalized or transferred to another hospital at their last assessment.												
h For the subgroup analyses, the model described in a was performed for each level of the subgroup without multiple imputation. P-value from the interaction between the subgroup variable and treatment group is also reported.												
i Estimate and 95% CI for the proportion are estimated using either logistic regression or TMLE.												
j Risk Differences calculated using the approach described in Ge.et al [1] or TMLE. CIs calculated using bootstrap or TMLE.												
k P-value from the logistic regression model or TMLE. For the interaction, P-value from interaction Type III test in subgroup analysis where the interaction between subgroup and treatment is being added to the logistic regression model.												

Tables with similar format:

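### If baseline steroid use is near 94%, the no-steroid row of the primary-endpoint subgroup analysis will often have an arm without events, and the planned Type III interaction p-value is then uninformative

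*Protocol*

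**What the plan says.** For the primary endpoint, SAP Section 6.4, Table 1 states: "Repeat the primary analysis for this endpoint within each of the following subgroups using the ITT population". Baseline steroid use is on that list. SAP Appendix 1, Table 4, footnote h fits the adjusted model separately at each level, without multiple imputation. Footnote k defines the interaction result as "P-value from interaction Type III test in subgroup analysis where the interaction between subgroup and treatment is being added to the logistic regression model".

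The SAP handles sparse data in two other places. In Section 8.1.3, "Categorical covariates with 90% of the subjects in one category will be dropped from the TMLE analysis". In Section 6.5.1.2, a group with no post-discharge events is given an event rate of 0.5 divided by the number of discharged subjects with known outcome. The supplied SAP has no counterpart for the logistic subgroup and interaction models: no minimum number of events, and no exact, penalised or likelihood-ratio alternative.

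Protocol Section 1.1 gives the only steroid figures, both from the concurrent trial: "As part of standard of care, 93.7% of subjects received corticosteroids, including dexamethasone" and "72.4% received remdesivir, and 69.1% received both". Protocol Section 6.5.1 permits steroids under local written standard of care or NIH guidelines and states no expected share for BET-B.

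**The concern.** A level holding about 6% of the subjects may have an arm without a single event. Maximum-likelihood logistic regression then has no finite odds ratio for that level. The estimated log odds ratio diverges and its standard error grows faster, so a Wald statistic for the interaction goes to zero and its p-value to 1. That p-value reflects a failed fit, but in a table it looks like evidence that the effect is the same with and without steroids.

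The failure can also be perverse. If one arm has few events because its true risk is low, a large difference between arms is what produces the empty cell. At stake is a planned, reported subgroup result in a trial intended as confirmatory. The primary test is not at stake.

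**Working it through.** **Inputs.** From Protocol Section 9.1: 400 subjects in the primary subgroup, control event rate 16% or 21%, odds ratio 2.5, two-sided alpha 0.049. From Protocol Section 5: equal arms (275 and 275), hence 200 per arm in the subgroup. From Protocol Section 1.1: 93.7% on steroids, hence 6.3% without. Applying that share to BET-B baseline use is an assumption.

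**1. The plan's own power.** Treated rate = odds/(1 + odds), with odds = control odds/2.5.
- 16%: (0.16/0.84)/2.5 = 0.0762, so the rate is 7.08%.
- 21%: (0.21/0.79)/2.5 = 0.1063, so the rate is 9.61%.

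A two-proportion test with 200 per arm gives 79.7% and 88.7% (pooled variance) or 80.3% and 89.2% (unpooled). This reproduces the stated 80% and "89% power if the control rate is 21%, if the odds ratio is 2.5 and a two-sided alpha=.049".

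**2. Size of the no-steroid level.** 400 x 0.063 = 25.2 subjects, or 12.6 per arm.
- Events at 16%: 12.6 x (0.16 + 0.0708) = 2.9.
- Events at 21%: 12.6 x (0.21 + 0.0961) = 3.9.
- All BET-B subjects receive remdesivir. Among remdesivir recipients in the concurrent trial, 69.1/72.4 = 95.4% had steroids. A 4.6% share gives about 18 subjects and 2.1 events at 16%.

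**3. Chance of an arm with no events.** P = a + b - ab, with a = (1 - treated rate)^n and b = (1 - control rate)^n.
- 16%, n = 13: a = 0.385, b = 0.104, P = 0.449. With n = 12, P = 0.487.
- 21%, n = 13: P = 0.303. With n = 12, P = 0.339.

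| Share without steroids | Expected events (16% control rate) | P(at least one arm has no events) |
|---|---|---|
| 4.6% | 2.1 | 62% |
| 6.3% | 2.9 | 45-49% |
| 10% | 4.6 | 25-27% |
| 20% | 9.2 | 5-7% |
| 30% | 13.8 | about 1% |

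**4. The Wald interaction p by event split.** Take 13 per arm without steroids, and 13 (active) and 30 (placebo) events among 187 per arm with steroids. The interaction estimate is the difference of the two log odds ratios; its variance is the sum of the eight reciprocal cell counts. For a 4/1 split (active/placebo):
- estimate = ln[(4 x 12)/(9 x 1)] - ln[(13 x 157)/(174 x 30)] = 1.674 + 0.939 = 2.613
- standard error = 1.252, z = 2.09, p = 0.037

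Other splits: 1/1 gives 0.54, 1/2 gives 0.91, 2/1 gives 0.20, 3/1 gives 0.08 and 5/1 gives 0.02. With no events in one arm, p is at least 0.98.

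**5. Rejection rates at nominal 5%, 6.3% share, 16% control rate.** Based on 1,500 simulated trials per scenario, with ordinal score, age and CRP in the model but unrelated to outcome. Figures in brackets are from a separate simulation. Reversed odds ratios are active against placebo, in non-users.

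| Effect in non-users | Wald | Likelihood ratio |
|---|---|---|
| No interaction | 0.6% | 4.3% |
| Reversed, odds ratio 2.5 | 28% (32%) | 43% (47%) |
| Reversed, odds ratio 5 | 60% (61%) | 75% (76%) |

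At a 21% control rate with no interaction, the figures are 1.0% and 5.4%.

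**6. The penalised test.** Based on 2,000 simulated trials per scenario in the unadjusted 2x2x2 model, with the Wald p set to 1 when a cell is empty. With no interaction, the Firth likelihood-ratio test rejects in 2.4%. At 10% placebo against 30% active in non-users, Wald rejects in 26% and Firth in 51%. At 5% against 40%, the figures are 33% and 83%. In that last case the placebo arm is empty with probability 0.95^12.6 = 0.52, so the low placebo risk disables the Wald test.

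The ordinary likelihood-ratio test rejected somewhat too often with no interaction at other shares (7.1% at 10% without steroids, 8.4% at 20%). That favours the penalised version.

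**The case against.** A reader might infer that the interaction p will be close to 1 whatever the data show. The documents and the arithmetic do not support that. With events in both arms the Wald test can reject: a 4/1 split gives 0.037. If lenzilumab were harmful in non-users, events in the level would rise and an empty arm would be less likely (14.5% of trials under reversal to an odds ratio of 2.5). Nor can one say that the level will have about 3 events. The 93.7% is any standard-of-care receipt in another trial, whereas the SAP subgroup is baseline use. At 80% baseline use the problem nearly disappears.

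Footnote k does not name the test statistic, and SAP Section 14 allows SAS or R. Wald is inferred from the PROC LOGISTIC code in SAP Section 6.5.1.3, where it is the default Type 3 test. General principles are deferred to a master SAP that was not supplied.

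The consequence is limited. The subgroup is outside the testing hierarchy in SAP Section 6.8. About 25 subjects can say little under any method. The Table 4 shell prints event-free counts and percentages by arm, so an empty arm would be visible.

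An extension to the Cox tables is not supported. SAP Table 1 omits baseline steroid use for time to ventilation or death. For sustained recovery, which includes it, the event is common: Protocol Section 1.1.1 reports about 75% of each arm discharged by Day 8 in the concurrent trial.

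All of this narrows the point. What remains is that the supplied SAP leaves the logistic subgroup models without protection against empty cells, although it foresees sparse data elsewhere.

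**Conclusion.** The concern holds conditionally. If baseline steroid use in BET-B is near 94%, the no-steroid row has about 25 subjects and 2 to 4 events. In about 30-34% of trials (21% control rate) to 45-49% (16% control rate), at least one arm has no events. The row then has no finite maximum-likelihood odds ratio, and a Wald interaction p of about 1 carries no information. The chance falls to about 25-30% at 90% steroid use and 5-7% at 80%.

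Across all trials with no interaction, the Wald test rejects in about 1% at a nominal 5%. Under reversal to an odds ratio of 2.5 it has about 28-32% power, against 43-47% for a likelihood-ratio test. The larger gain at 5% against 40% belongs to an extreme scenario and should not be read as typical.

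These results assume that the external steroid share carries over, that the Type III test is Wald, and that the Section 9.1 event rates apply in non-users unless a scenario says otherwise. The primary analysis and its alpha are not affected.

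**What to change.** In SAP Appendix 1, Table 4, change footnotes h and k. Fit the logistic subgroup and interaction models by Firth penalised likelihood with profile-likelihood confidence intervals. Take the interaction p-value from a penalised likelihood-ratio test comparing the models with and without the interaction, in place of the Type III Wald test.

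The cost is two footnotes and a program option, with no effect on data collection or patients. The downside is that subgroup odds ratios are shrunk slightly toward 1. The primary analysis, its alpha and the Cox tables stay as they are.
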